9.4.3 ANALYSIS OF THE SECONDARY ENDPOINT(S)

- The difference between the active and sham treatment groups in mean headache intensity during study period

Repeated measures mixed models will be used to describe the difference between the active and sham treatment groups in mean headache intensity during NSCU length of stay. Pain will be modeled as a function of treatment group and measurement time. Subject will be included as a random effect. Least squared means will be used to estimate the treatment effect.

- The difference between total overall morphine equivalence dosage between the active and sham group per subject during study

Total overall morphine equivalence dosage in the active and sham treatment groups will be compared using analysis of covariance (ANCOVA) with adjustment for number of days in study.

-Opiate related adverse events (such as urinary retention, constipation, sedation, nausea, vomiting and pruritis)

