The Biostatistics Unit at the Feinstein Institute for Medical Research [BU-FIMR] will develop a randomization plan for the study using the Biostatistics Randomization Management System [BRMS]. BRMS is a secure, HIPAA-compliant, web-based application that allows investigators to randomize subjects into randomized clinical trials (RCTs) using a personal computer with internet access. A randomization allocation will be generated by the BU-FIMR using the method of permuted blocks. Details of the randomization procedure, including required record keeping will be further developed upon approval of the protocol. The treatment group will receive 2, 2 minute stimulations every 5 hours delivered by a blinded provider. The person assessing the pain intensity, vital signs, and giving pain killers and the participants will be blinded. Pain will be rated pre and post stimulation by the blinded caregiver. During NSCU stay at each stimulation, patients will be on continuous telemetry, and vital signs will be recorded before and at the end of the treatment and hourly for the rest of the day by the blinded caregiver. The control group will receive a sham device, the device is physically identical to the active device, and however no stimulation will be delivered. Patients in either group will be informed that they might feel a tingling sensation or muscle twitch with either device. Before the stimulation is initiated, vital signs will be checked. This includes HR, SBP, MAP, and oxygen saturation. If vital signs are stable, defined as HR>60 beats per minute, SBP> 100 mmHg, MAP> 60 mm HG, and saturation > 90% on room air, nasal cannula or face mask, the stimulation will be provided. In addition, both groups will receive standard of care abortive medications. Pain is usually assessed every 4 hours and as needed, and abortive medications are given depending on the intensity of the headache. 40 patients will be enrolled, and VNS will be performed for up to 10 days.

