4.4 END OF STUDY DEFINITION

The study intervention will be up to 10 days in length. Vagus stimulation will be performed 4 times daily (approximately at 6:30AM, 11:30AM, 4:30PM and 9:30PM). Data collection will continue till hospital discharge. If the participant becomes hemodynamically unstable, defined as hypotension requiring vasopressors the VNS will be held for safety purposes. However, it will be resumed, once the patient is stabilized, off vasopressors for 48 hours. If the patient is being hemodynamically augmented for symptomatic vasospasm, n-VNS will not be withheld as the beneficial effects of n-VNS on symptomatic vasospasm will be investigated in this study.

Participants must fulfill all of the inclusion criteria in order to be eligible for the study:

- Established signed and dated informed consent form
- Can be enrolled within 5 days of cerebral aneurysm treatment.
- CT of the head revealing blood in the subarachnoid space
- Subject has ruptured cerebral aneurysm or SAH patients who do not have vascular malformation on cerebral angiogram.
- Subject is male or female 18 -75 years of age
- Subject is alert able to verbalize pain at the time of enrollment
- Subject reports pain of 7 and greater on a 10 Point Pain numeric rating scale or presenting with severe headache.
- Female of reproductive age must have a negative pregnancy test (Urine or blood test)

nVNS will only be performed if vital signs are stable (HR>60, SBP> 100 mmHg, MAP> 60 mmhg, and saturation > 90% on room, nasal cannula or face mask). Then the vagus nerve will be stimulated.

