
Screening involves reviewing the medical records following HIPPA regulation for: Age, gender, ethnicity, presence of aneurysm, day of rupture, etiology of the SAH if not aneurysmal, radiologic (Angiogram, CT head) and medical history before and after the aneurysm is secured, Glasgow coma score before and after aneurysm repair, modified fisher scale (mFS), Hunt-Hess grade (HHS), time of ictus, history of alcohol and drug abuse, presence of hydrocephalus on head CT, presence of an external ventricular drain (EVD), date of EVD placement, new HHS after EVD placement, clipping or coiling. Medical records will be reviewed for the past medical history (pacemaker, defibrillator, history of CHF, arrhythmias, cervical carotid disease, history of a headache disorder like migraine or cluster headache), physical examination, labs will be reviewed which includes but not limited to pregnancy test and urine toxicology. Headache intensity and opiate, steroids and acetaminophen usage are recorded in the electronic medical record. The presence of vasospasm and delayed cerebral ischemia will be noted. Once found eligible satisfying the inclusion and exclusion criteria, and informed consent signed, patients will be randomized to either the treatment group or the control group. The same data will be recorded for both groups. The treatment period will start once admitted in the NSCU and will last for up to 10 days.

During the NSCU stay, patients areevaluated for pain every 4 hours. If vital signs are stable (SBP> 100 mmHg and HR> 60 beats per minutes with no arrhythmia on telemetry, MAP> 60 mmHg and oxygen saturation > 90%) patient will receive either the treatment (nVNS) or the Sham device every 5 hours. Headache intensity will be evaluated every four hours. In addition, vital signs will be noted just after stimulation, and hourly afterwards or as ordered by the physician. The daily mean morphine equivalence dosage will be recorded. Concomitant medications will be recorded.

During the ICU length of stay, the following will be assessed and recorded per standard of care :

- Transcranial dopplers (TCD)
- Neuroimaging (CT head, MRI brain, angiograms, CT perfusion with permeability study)
- EVD weaning and day of start of weaning
- Presence of vasospasm, delayed cerebral ischemia, Central fever, Cerebral salt wasting. These are usually recorded in the medical record.
- Urinary retention documented as frequent straight catheterization for more than 3 days

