9.4.2 ANALYSIS OF THE PRIMARY EFFICACY ENDPOINT(S)

-The difference between the active and sham treatment groups in daily mean morphine equivalence dosage during the study

Repeated measures mixed models will be used to describe the difference between the active and sham treatment groups in morphine equivalence dosage during NSCU length of stay. Morphine equivalence dosage will be modeled as a function of treatment group and measurement time. Subject will be included as a random effect. Least squared means will be used to estimate the treatment effect.

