The primary efficacy variable, the daily morphine equivalency dose by visit, will be analyzed using a restricted maximum likelihood (REML)-based repeated measures approach (Mixed Model Repeated Measures (MMRM)). The model for analysis will include fixed, categorical effects of treatment, visit, and treatment by visit interaction, as well as the continuous, fixed covariates of baseline value. An unstructured (co)variance structure will be used to model the within-patient errors. If this analysis fails to converge, compound symmetry will be tested. The (co)variance structure converging to the best fit, as determined by Akaike's information criterion will be used as the primary analysis. The Kenward-Roger approximation will be used to estimate denominator degrees of freedom. The primary treatment comparison will be the contrast between treatments at Day 14 for active treatment versus sham treatment. Treatment group differences contrasts will be computed overall and for each analysis visit (i.e., Day 1, Day 2, Day 3, ..., Day 14) and displayed with the respective 95% CIs. Significance tests will be based on least-squares means and Type III sum-of-squares, using two-sided tests at the 0.05 level (two-sided 95% confidence intervals). No imputed values will be used for the MMRM analysis.

Sensitivity analysis

All analyses on the primary efficacy endpoint will be repeated on the PPS

Additionally, the missing data for the mean daily morphine equivalency dose will be computed using an LOCF algorithm and analyzed using the MMREM model.

Analysis of Secondary and Exploratory Variables

For each of the variables mentioned above, the randomization group difference will be examined using a T-test for continuous variables, and Fisher's exact test for categorical variables at each visit.

Analysis of safety variables

Treatment group differences in the occurrence of serious adverse events will be evaluated using Fisher's exact test.

Adverse events:

The primary safety endpoint of this study is the overall incidence of device related serious AEs. AEs and SAEs will be summarized and presented as proportions and respective 95% exact binomial confidence intervals (CIs).

Frequency and percentage of subjects experiencing a specific adverse event will be tabulated by system organ class, preferred term, and treatment group.

Summary tables and subject data listings will be provided.

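### Headache intensity is analysed without adjustment for pre-treatment pain in both documents, which costs precision (not validity) by an amount the documents do not let us fix

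*Protocol*

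**What the plan says.** The two documents give different methods for mean daily headache intensity, and neither has a baseline term.

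- Protocol 9.4.3: "Pain will be modeled as a function of treatment group and measurement time". The only other term is the patient: "Subject will be included as a random effect".
- SAP, Analysis of Secondary and Exploratory Variables: "the randomization group difference will be examined using a T-test for continuous variables", applied at each visit. Mean daily headache intensity is one of the listed secondary variables. For these variables, baseline enters only through descriptive summaries of change.

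The opioid-dose outcome is treated differently. The SAP's mixed model has treatment, visit and their interaction, "as well as the continuous, fixed covariates of baseline value". Protocol 9.4.2, in a version dated January 2023 and so later than the May 2022 SAP, has no such term: "Morphine equivalence dosage will be modeled as a function of treatment group and measurement time".

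Pre-treatment pain is available from several places. Protocol 4.1 plans it directly: "Pain will be rated pre and post stimulation by the blinded caregiver". Pain is also an entry criterion: "Subject reports pain of 7 and greater on a 10 Point Pain numeric rating scale or presenting with severe headache". Protocol 8.1, on screening, adds: "Headache intensity and opiate, steroids and acetaminophen usage are recorded in the electronic medical record".

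**The concern.** Headache intensity is the outcome named in the study hypothesis (Protocol 1.1 and the SAP overview). With about 20 patients per arm, the arms can start at visibly different pain levels by chance. An analysis without the starting level leaves that difference in the estimate and carries more residual variance than it needs to. The random subject effect does not help, because it models correlation within a patient and does not correct a difference between arms.

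The stakes go beyond one secondary comparison. The SAP tests treatment differences at two-sided 0.05, and both documents say the pilot exists to size a larger trial. The baseline-outcome correlation and the adjusted residual variance feed directly into that calculation, and the analysis as planned yields neither.

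**Working it through.** **Figure to reproduce.** None. The documents give no power, effect size, standard deviation or correlation.

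**Inputs from the documents.** About 40 patients (SAP overview), allocated 1:1 (Protocol 6.3), so n = 20 per arm; up to 10 days of stimulation (Protocol 4.4); two-sided 0.05 (SAP, General approach).

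**Assumed inputs.** Day-to-day within-patient correlation r = 0.3, 0.5 or 0.7, equal for all pairs of days; a one-day baseline.

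**Formulas.** Let rho be the correlation of baseline with the outcome analysed.
- Ratio of adjusted to unadjusted standard error: sqrt(1 − rho²).
- One visit, as in the SAP test: rho = r.
- Mean of T = 10 days, as in the protocol model: rho = r / sqrt((1 + 9r)/10), which gives 0.493, 0.674 and 0.819.
- Estimating the slope multiplies the variance by 1 + 1/(N − 4) = 37/36 at N = 40.

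**Results** (reduction in standard error):

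| Case | r = 0.3 | r = 0.5 | r = 0.7 |
|---|---|---|---|
| One visit, unrestricted baseline | 5% (ratio 0.954) | 13% (0.866) | 29% (0.714) |
| 10-day mean, unrestricted baseline | 13% (0.870) | 26% (0.739) | 43% (0.573) |
| 10-day mean, baseline 7 or more (simulated, day SD 2.2) | 3% | 7% | 18% |
| One visit, baseline 7 or more | 0 to 1% | 3 to 5% | 9 to 15% |

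The first two rows leave out the slope cost. With it, the one-visit ratios become 0.967, 0.878 and 0.724.

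The last row uses simulated pain distributions in which restriction to 7–10 lowers rho from 0.3 to 0.16–0.21, from 0.5 to 0.29–0.36 and from 0.7 to 0.45–0.54. The slope cost is included. For example, at rho = 0.36, sqrt((1 − 0.130) × 37/36) = 0.946. The restricted figures move by a few percentage points with the average pain level assumed.

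**Break-even.** Adjustment gains nothing when (1 − rho²) × 37/36 ≥ 1, that is when rho ≤ sqrt(1/37) = 0.16. If only 15 per arm reach the mITT set, on which the SAP analyses secondary variables, the threshold is sqrt(1/27) = 0.19.

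**Chance imbalance.** The between-arm difference in mean baseline has standard deviation sqrt(2/20) = 0.32 baseline SDs. It exceeds 0.3 SD with probability 34% and 0.5 SD with probability 11%. The shift in the unadjusted estimate is slope times imbalance, so a 0.5 SD imbalance moves it by 0.15, 0.25 or 0.35 outcome SDs at rho = 0.3, 0.5 or 0.7. In points, with an assumed slope of 0.5 and a baseline SD of 1.1 (about what the simulations give for scores of 7–10), the 95% range is ±1.96 × 1.1 × 0.316 × 0.5 = ±0.34. The largest SD possible on 7–10 is 1.5, which gives ±0.46.

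**Check on the random subject effect.** In a simulated random-intercept model (10 days, intraclass correlation 0.5, 20 per arm), adding baseline cut the standard error of the treatment effect by 2, 7, 15 and 25% at single-day correlations of 0.2, 0.3, 0.4 and 0.5. Both estimators averaged to zero under no effect. So the random effect does not do the work of a baseline term, and leaving that term out causes no bias.

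**The case against.** The strongest reply is that this is a preference about efficiency. Headache intensity is a secondary endpoint, the protocol plans descriptive comparisons for it, and both documents say there are no statistical hypotheses. Two parts of this stand: no error rate is compromised, and the endpoint is not the primary one. It does not dispose of the point, because the SAP does test differences at 0.05 and the pilot's estimates are meant to size the next trial.

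A reader might infer that the unadjusted comparison is biased, or that chance imbalance is a further error on top of the wider standard error. Neither holds. Under 1:1 randomisation the estimate is unbiased, and the conditional shift is part of the sampling variation that the unadjusted confidence interval already covers. Nor does imbalance enter at full size: it is multiplied by the slope.

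A reader might also take 26 to 43% as the precision being lost. That needs a full 10-day mean, an unrestricted baseline and a correlation the documents do not supply. Ten days is a maximum, the SAP tests one visit at a time, and entry at 7 or more narrows the baseline. The other entry route, presentation with severe headache, does not clearly restore the full range.

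Finally, the data are not guaranteed to be complete. The Schedule of Activities has no pain-score row, and a patient admitted for severe headache may have no numeric entry score. A 24-hour pre-treatment average could, for the earliest starters, reach back to the aneurysm procedure. These objections bear on how the covariate is defined, and the pre-stimulation rating in Protocol 4.1 answers them.

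**Conclusion.** The point holds as a loss of precision in a secondary endpoint. Both documents omit pre-treatment pain, no reason is given, and the SAP already adjusts for baseline in its opioid-dose model.

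The size is uncertain. Across assumed correlations of 0.3 to 0.7, the standard error could fall by 5 to 29% at one visit or 13 to 43% for a 10-day mean with an unrestricted baseline. It falls by about 3 to 18% for the mean if baseline is limited to 7 or more, and not at all if the baseline-outcome correlation is below about 0.16. With the stated entry criterion, the lower figures are the safer expectation. Even at zero correlation the loss from adjusting is about 1% in standard error (sqrt(37/36) = 1.014), so the change is worth making.

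**What to change.** - **One method for headache intensity.** A covariate cannot be added to a t-test. Replace the SAP's per-visit t-test for this variable with the SAP's own repeated-measures model (treatment, visit, treatment by visit) plus baseline pain, and write the same model into Protocol 9.4.3.
- **One definition of baseline pain.** Use the last numeric pain rating before the first stimulation, for every patient. The SAP's present baseline is the Day 1 value, which is not stated to precede stimulation, and Day 1 is also an analysis visit. Use only post-stimulation ratings as outcomes. Confirm that the case report form captures the pre-stimulation score.
- **Opioid dose.** Add the baseline dose term to Protocol 9.4.2 so that it agrees with the SAP's primary model.

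The cost is one degree of freedom in the headache model, a short rewrite of the SAP's secondary analysis and a line in each of two protocol sections. No assessment is added, since the pre-stimulation rating is already planned. The change should be fixed before unblinding.

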9.4.4 SAFETY ANALYSES

The primary safety endpoint of this clinical investigation is the overall incidence of devicerelated serious AEs. The primary safety analysis will be summarized and presented as proportions and respective 95% exact binomial confidence intervals (CIs). The rate of opiate related adverse events will similarly be presented as proportions and respective 95% exact binomial confidence intervals.

Frequency and percentage of subjects experiencing a specific adverse event will be tabulated by system organ class, preferred term, and treatment group. Summary tables and subject data listings will be provided.

9.4.5 BASELINE DESCRIPTIVE STATISTICS

9.4.6 PLANNED INTERIM ANALYSES

A safety interim analysis may be considered if deemed necessary by the principal investigator

10 SUPPORTING DOCUMENTATION AND OPERATIONAL CONSIDERATIONS

10.1 REGULATORY, ETHICAL, AND STUDY OVERSIGHT CONSIDERATIONS

10.1.1 INFORMED CONSENT PROCESS

10.1.1.1 CONSENT PROCEDURES AND DOCUMENTATION

Informed consent is a process that is initiated prior to the individual's agreeing to participate in the study and continues throughout the individual's study participation. Consent forms will be Institutional Review Board (IRB)-approved and the participant will be asked to read and review the document. The investigator will explain the research study to the participant and answer any questions that may arise. A verbal explanation will be provided in terms suited to the participant's comprehension of the purposes, procedures, and potential risks of the study and of their rights as research participants. Participants will have the opportunity to carefully review the written consent form and ask questions prior to signing. The participants should have the opportunity to discuss the study with their family or surrogates or think about it prior to agreeing to participate. The participant will sign the informed consent document prior to any procedures being done specifically for the study. Participants must be informed that participation is voluntary and that they may withdraw from the study at any time, without prejudice. A copy of the informed consent document will be given to the participants for their records. The informed consent process will be conducted and documented in the source document (including the date), and the form signed, before the participant undergoes any study-specific procedures. The rights and welfare of the participants will be protected by emphasizing to them that the quality of their medical care will not be adversely affected if they decline to participate in this study. If the patient is physical disabled and is unable to sign the informed consent, oral consent process for more than minimal risk research will be followed as stated in the HRPP Policy and Procedures Manual. If patient decision capacity is in doubt, a mini mental state examination will be performed, and if the score is <24, the signature of a healthcare Agent, guardian or next of kin will be required with an assent of the patient.

Via Telephone/Email/Mail (one or in combination) for LAR's that are off-site:

Investigator may contact (or be contacted by) a potential LAR by telephone or email to discuss participation in a research study. Investigator must provide LAR with all the information contained in the consent form. Investigator will answer any questions regarding the research study and giveLAR ample time to consider participation in the study. (May require follow-up email/phone conversation). IfLAR indicates interest in participating in the research study, the LAR will be informed of the next steps necessary to provide informed consent

- a. A consent form will be sent to the LAR by regular mail (if no email access), an email attachment
- b. The LAR must read the consent form and call or email the investigator if he/she wishes to discuss the research and resolve issues/questions

If LAR agrees to participate in research, he/she should sign the consent form and return it to the investigator by one the following methods:

- c. Mail or fax hard copy to the site
- d. Return a picture/image of signed consent form
- e. Scan the signed consent form and return it to the investigator as an email attachment.
- f. If the LAR received the consent electronically but does not have access to printing, the following will apply
 - i. The LAR will verbally consent (with a witness on the phone) and respond via email documenting the confirmation he/she consents.
 - ii. A copy of the email confirming consent will be filed in the subject's binder.
 - iii. LAR may sign and return the ICF on a future date.

An enrollment note must be written by the investigator documenting all phone conversations with the subject. Printouts of any email correspondence must be placed in the subject's file. After the signed consent form is received, investigator will sign the consent form and date the signature with the current date. The investigator should add a note detailing the date discrepancy of the signatures. A copy will be made and sent to the LAR for his/her records.

If a consent form is returned missing a signature, the participant will be notified by phone or email. A copy will be made and kept in the participant's file and the original will be sent back to the participant for completion and resubmission to the investigator.

1. Documentation required

- a. How was the ICF transmitted to the LAR (email, mail, fax)
- b. How was the LAR signature obtained (e-signature, scanned and email back, mailed back, took a picture of signature page emailed/text back, verbal assent with witness present and subsequent email confirmation)
- c. Enrollment note written by investigator documenting consent discussions by phone with the LAR
- d. Statement describing how fully signed consent copy was given to LAR

